- 3.2.18 Other serious illness(es) involving the cardiac, respiratory, CNS, renal, hepatic or hematological organ systems which might preclude completion of this study or interfere with determination of causality of any adverse effects experienced in this study
- 3.2.19 Prior investigational therapy (medications or devices) within 4 weeks of treatment. Furthermore, other investigational therapy is not permitted during the treatment phase.

- 3.2.20 Prior use of ketoconazole for the purposes of prostate cancer therapy for greater than 1 month
- 3.2.21 Known history of HIV.
The effects of J591 are unknown in this population. Furthermore, ketoconazole has many well-described drug-drug interactions which could affect antiviral therapy. If necessary, this population will be studied separately.
- 3.2.22 Currently active other malignancy other than non-melanoma skin cancer.
Patients are considered not to have “currently active” malignancy if they have completed any necessary therapy and are considered by their physician to be at less than 30% risk of relapse.
 - Known history of known myelodysplastic syndrome
- 3.2.23 Adrenal hormone inhibitors (other than ketoconazole) within 4 weeks prior to study enrollment.
- 3.2.24 Finasteride (Propecia® or Proscar®) or dutasteride (Avodart®) within 4 weeks of enrollment.
- 3.2.25 Patients on corticosteroids prior to enrollment must have either discontinued and shown biochemical progression or have biochemical progression on a stable dose

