13. STATISTICAL CONSIDERATIONS

13.1 Study Design/Endpoints

The study is a randomized phase 2 study with a 2:1 ratio favoring ^{177}Lu -J591, with stratification by investigational site and mode of primary therapy (radiation vs surgery). Randomization will be performed by using a series of randomized blocks of 6 within each participating site/primary therapy stratum (with a 2:1 allocation ratio). This will provide assurance that after six patients are enrolled in any given participating site/primary therapy stratum, there will be four patients assigned to the combination regimen (Group 1) and two patients assigned to the single regimen (Group 2). This procedure will allow for each site to contribute similar numbers of ^{177}Lu -J591/ketoconazole patients and ^{111}In -J591 (placebo)/ketoconazole patients within the defined participating site/primary therapy strata.

The primary endpoint is the proportion free of metastases in each group at 18 months. Ninety-five percent confidence intervals (95% CI) will be estimated for the 18-month MFS proportion in both groups via binomial proportions. The MFS proportion will also be descriptively evaluated at 12, 24, 30, and 36 months in each group.

MFS will be measured from the start of the treatment to the date of either documentation of metastatic disease or death. All treated patients will be observed for a minimum of 18 months. The 18-month MFS proportion with ketoconazole + ^{111}In -J591 has been estimated to be 50% {521 Smith, M.R. 2005}; therefore, the target 18-month MFS proportion for the combination of ketoconazole + ^{177}Lu -J591 regimen is hypothesized to be 80%. An intent to treat analysis will include all randomized subjects. However, we will also analyze subjects who received study-drug. This subset will be those subjects who met eligibility requirements, have initiated therapy, and were not removed from the study for non-compliance or patient withdrawal within the first 4 weeks, and received infusion of study drug.

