With approximately 34 patients in the ketoconazole+J591 arm and 17 patients in the ketoconazole monotherapy arm (2:1 allocation), this design will allow for the detection of a 30% absolute difference in the 18-month MFS proportion between the ketoconazole+J591 arm and the ketoconazole monotherapy arm (80% vs. 50%, respectively) with $\geq 80\%$ power and a one-sided alpha level of 10%. An additional 10% will be enrolled to account for loss to follow up (total projected number of subjects to be randomized = 55). A 95% CI for the difference in the 18-month MFS proportion between the two treatment arms can be constructed to be within $\pm 18\%$ of the true difference in 18-month MFS proportions.

13.1.1 ^{111}In -J591 as placebo

We have chosen to infuse ^{111}In -J591 as a placebo in this double-blind study. The infusion procedures and characteristics of this compound are similar to ^{177}Lu -J591. In addition, ^{111}In -J591 will allow imaging studies to be performed. Because ^{111}In is a pure gamma-emitter, there will be no treatment effect as in the beta emission with ^{177}Lu . It is theoretically possible that by infusing ^{111}In -J591, there will be a treatment effect by ADCC, thereby diluting the proportional effect of ^{177}Lu -J591 in the experimental arm. However, clinically meaningful ADCC is not expected, as it has been demonstrated at

much higher doses of the J591 antibody (122), and by giving equal antibody doses in each study arm, we will be able to truly evaluate the effect of ^{177}Lu radioimmunotherapy.

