13.4 Analysis of Secondary & Exploratory Endpoints

Secondary endpoints include biochemical (PSA) response rate, duration of PSA response, biochemical (PSA) progression, time to biochemical (PSA) progression, time to biochemical (PSA) progression above baseline, overall survival, and toxicity. We anticipate that the 95% confidence interval around the PSA response rate will be within $\pm 9\%$ of the true value for Arm 1 and within $\pm 15\%$ of the true value for Arm 2. Time to biochemical (PSA) progression, time to biochemical (PSA) progression above baseline, median MFS-time, and overall survival will be estimated using the Kaplan-Meier method, and 95% confidence intervals will be calculated using Greenwood's formula.

The frequency of subjects experiencing toxicities will be tabulated. Toxicities will be assessed and graded according to CTCAE v. 4.0 terminology. Exact 95% confidence intervals around the toxicity proportions will be calculated to assess the precision of the obtained estimates.

Imaging studies: The possibility of identifying sites of metastatic disease not apparent on conventional imaging (CT/MRI abdomen/pelvis, bone scan, and CXR) will be confirmed with serial imaging. Any potential metastatic site on J591 imaging will be followed over time by conventional imaging. Sites of disease appearing on J591 scan and subsequently confirmed by conventional imaging will be labeled as positive. Any site apparent on J591 scan that is subsequently biopsied as part of standard care and confirmed to be metastatic prostate cancer will be labeled as definite. Sites of disease appearing on J591 scan without any corroborating evidence (conventional imaging or biopsy) will be labeled as possible.

Adrenal hormonal levels: Baseline adrenal hormonal levels will be categorized by median baseline levels found in CALGB 9583 (60, 61). In addition, as this may be a different patient population, we will analyze by median as well as quartiles. We will correlate levels with time to radiographic metastatic disease as well as PSA response and overall survival. Changes in adrenal hormone levels will be analyzed with time (baseline, 1 month, 6 months, at progression).

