Plasma markers of hemostasis/fibrinolysis/angiogenesis: Baseline levels will be categorically analyzed by median as well as in quartiles and will be correlated with clinical endpoints (time to mets, survival, PSA response). We will also perform exploratory analyses using these values as continuous variables. In addition, a description of changes in levels of these markers with time/treatment will be reported. We will explore changes (decreases) by 50% (and median decrease) in correlation with outcome/response.

CTC's: Change in CTC counts will be summarized descriptively. Baseline counts ≥ 5 CTCs vs < 5 (per 7.5 mL) will be analyzed for time to metastatic disease in the overall population. We will also analyze changes with therapy: Decrease from ≥ 5 to < 5 , increase from < 5 to ≥ 5 , and stable categorical counts with respect to primary and secondary efficacy endpoints.

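### Section 13.4 should add continuous analyses of baseline adrenal hormones and CTCs to the planned cut-points, and should stratify post-infusion CTC change by arm

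*Combined protocol and SAP*

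**What the plan says.** **Adrenal hormones.** Section 13.4: "Baseline adrenal hormonal levels will be categorized by median baseline levels found in CALGB 9583". The same paragraph adds the trial's own median and quartiles. It then says levels will be correlated with time to metastasis, PSA response and survival, naming no scale or method. Section 2.4.1 is more specific. Time to metastasis and survival are analysed by category, while for PSA response the median baseline level is compared between responders and non-responders. Changes in hormone level are analysed over time, with no planned link to outcome.

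**CTCs.** Baseline counts, split at 5 cells per 7.5 mL, "will be analyzed for time to metastatic disease in the overall population". Change in counts is summarised descriptively. Crossing the 5-cell line in either direction, or staying on one side, is then related to the primary and secondary efficacy endpoints. No arm term, stratification or landmark time is given. Under section 9.1.3.1 and the study calendar, the C1D1 and C2D1 samples precede the J591 infusion; the C3D1, PSA-progression and end-of-study samples follow it.

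**Plasma markers.** After the median and quartile analyses, 13.4 adds: "We will also perform exploratory analyses using these values as continuous variables".

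**The concern.** There are two separate issues.

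1. **Scale.** Cutting a graded marker discards information, and a small trial has little to spare. The adrenal objective is a secondary objective (section 1.2) meant to validate a published CALGB 9583 result (2.4.1), so an avoidable loss makes a null result hard to read. The 5-cell cut comes from metastatic disease (2.4.3), whereas this trial enrols men without radiographic metastases. Few men may exceed it, and an unbalanced cut loses more. The plan already accepts a continuous analysis for the plasma markers, so its absence for the other two looks like an omission.

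2. **Arm.** The trial expects 177Lu-J591 to lower metastasis risk, and it may also lower CTCs. If so, men whose CTCs fall will disproportionately be 177Lu men, and pooling the arms can show an association between CTC fall and outcome that is only the treatment effect.

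**Working it through.** **The plan's own figures.** No power or precision is stated for the adrenal or CTC association analyses. The only related figure is the primary power. Section 13.1: "With approximately 34 patients in the ketoconazole+J591 arm and 17 patients in the ketoconazole monotherapy arm (2:1 allocation"; "80% vs. 50%, respectively"; "a one-sided alpha level of 10" per cent. The average proportion is (34×0.8 + 17×0.5)/51 = 0.70. The null SE is √[0.7×0.3×(1/34 + 1/17)] = 0.1361, and the alternative SE is √(0.16/34 + 0.25/17) = 0.1393. Power = Φ[(0.30 − 1.2816×0.1361)/0.1393] = 81.6%, so the stated 80% or more reproduces.

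**Information kept by a cut** (assumed: normal marker, linear effect). For one cut with share p above it at normal quantile z, the share kept is φ(z)²/[p(1−p)].

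| Cut | Kept | Lost |
|---|---|---|
| Median, p = 0.5 | 0.3989²/0.25 = 0.637 (= 2/π) | 36% |
| 5 cells, p = 0.3 | 0.3477²/0.21 = 0.576 | 42% |
| 5 cells, p = 0.2 | 0.2800²/0.16 = 0.490 | 51% |
| 5 cells, p = 0.1 | 0.1755²/0.09 = 0.342 | 66% |
| Quartiles, best scores | (1.2711² + 0.3247²)/2 = 0.861 | 13.9% |
| Quartiles, scores 1 to 4 | 1.0345²/1.25 = 0.856 | 14.4% |

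The shares at or above 5 cells are assumptions. If the CALGB median falls between this trial's 30th and 70th percentiles, that cut loses 36% to 42%.

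**In power terms** (two-sided 5%). Where a continuous test has 80% power, the median split has Φ(√0.637×2.80 − 1.96) = 61%, a quartile trend test 74%, and a 3-df quartile test 57%. Section 13.4 does not say which quartile test is meant.

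**In events.** At 18 months, 34×0.2 + 17×0.5 = 15.3 (metastases or deaths, since 13.1 counts both in MFS). With Φ[√events × ln(HR) − 1.96] and an assumed HR of 2.0 per SD, power is 77% continuous and 58% with a median split. With constant hazards and 36 months for everyone, events are 34×(1 − 0.8²) + 17×(1 − 0.5²) = 25.0, giving 93% and 79%.

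**Pooling the arms for CTC change.** Take the design rates (20% and 50% with metastasis) and no association within either arm.

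- *Every man able to convert, conversion 60% on 177Lu and 20% on control (assumed):* 18-month MFS is 75.7% in converters and 65.0% in the rest, odds ratio 1.68. In 20,000 simulated trials of 34 and 17, the pooled test rejects 12.7% of the time at a nominal 5%, against 4.8% when stratified by arm. Over assumed rates from 50%/10% to 80%/20%, the pooled test rejects 12.6% to 25.4%.
- *Only men starting at 5 or more can fall below 5; 30% do so, of whom 60% and 30% convert (assumed):* decliners are 18% and 9% of the arms. Metastasis risk is (34×0.18×0.2 + 17×0.09×0.5)/(34×0.18 + 17×0.09) = 1.989/7.65 = 26% in decliners and 13.311/43.35 = 31% in the rest. The pooled test rejects about 4% of the time, and no more than about 7% at the other rates tried.
- *Equal conversion in both arms:* odds ratio 1.00, rejection 5.1%.

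**The case against.** The case for leaving the plan alone has real content.

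- **Not everything is cut.** A reader might infer that adrenal hormones are analysed only in categories. Section 2.4.1 compares uncut levels for PSA response, so the gap is confined to time to metastasis and survival. Even there, 13.4's reference to correlating levels is ambiguous.
- **The loss is not always over a third.** That holds for single cuts. Quartiles used as a trend lose about 14%, although no trend test is named and a 3-df test would give up the advantage.
- **Fifteen events is a floor.** It might be inferred that the adrenal objective is clearly underpowered. But 18 months is the minimum observation, MFS is described to 36 months, and the outcome is time to metastasis. The lower power figures are the pessimistic end, and the hazard ratio behind them is assumed.
- **The published cut has a purpose.** Validating a median-based result justifies keeping the pre-set CALGB median. This stands: the continuous term should be added, not substituted.
- **Arm mixing is narrow.** It does not reach baseline values, which are independent of randomised arm in expectation, nor C1D1-to-C2D1 CTC change, which precedes the infusion. Nor does it reach adrenal changes, which have no planned link to outcome and whose 1-month sample is pre-infusion. The second pooling example shows that the distortion may be small.
- **Prior exposure.** Criterion 3.2.23 excludes "Adrenal hormone inhibitors (other than ketoconazole) within 4 weeks prior to study enrollment", 3.2.20 excludes only more than a month of earlier ketoconazole, and 3.2.25 admits men on stable corticosteroids. Some baseline hormone values could therefore already be suppressed. The documents give no frequency, so this supports a sensitivity analysis and not exclusion.

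**Conclusion.** The point holds in a limited form. Baseline CTCs have only the 5-cell split, and baseline adrenal hormones have only median or quartile groups for time to metastasis and survival, while the neighbouring plasma markers also get a continuous analysis. The loss is 36% for a median split, 42% to 66% for the CTC cut and about 14% for a quartile trend. These figures assume a normal marker, a linear effect and 10% to 30% of men at 5 or more cells. If many men have zero CTCs, the normal model is only a rough guide.

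Post-infusion CTC change lacks an arm term, so a treatment effect could be read as a biomarker effect. The direction follows whenever treatment moves both in the expected way. The size rests on assumed conversion rates and ranges from negligible to a false-positive rate several times nominal.

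The adrenal objective is secondary and the CTC objective exploratory (1.3). The primary comparison does not depend on either.

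**What to change.** In section 13.4:

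1. Add log(level) for each adrenal hormone and log(CTC+1) as continuous terms in the time-to-event models, alongside the CALGB median and the 5-cell cut. If quartiles are kept, name the test.
2. Fit models of post-infusion CTC change stratified by arm, from a landmark at C3D1 and among men still free of the event then. This also settles which sample defines change; end-of-study samples are taken at metastasis itself and cannot predict it.
3. Optionally, add a sensitivity analysis flagging men exposed to ketoconazole or corticosteroids in the 4 weeks before the baseline adrenal sample. Prior hormonal therapy dates and concurrent medications are already recorded at screening (10.1).

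The cost is SAP wording and a few extra model fits. No new data, samples or patients are needed.

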13.5 Reporting and Exclusions

- 13.5.1 **Evaluation of toxicity.** All patients will be evaluable for toxicity from the time of their first treatment on study. Toxicity of radiolabeled J591 in this population will be evaluated from the time of J591 administration.
- 13.5.2 **Evaluation of response.** All patients included in the study will be assessed for response to treatment if they have received at least 4 weeks of therapy with ketoconazole and received radiolabeled J591. Subjects dropping out of the study prior to J591 administration will be replaced.

14 Inclusion of Women and Minorities

Women are excluded from the protocol because prostate cancer is a disease of men. No exclusion based upon race/ethnicity will occur.

15. Study Personnel

Study Chair ([name]): Responsible for patient recruitment and over-all clinical management, protocol design and coordination, assessment of adverse events, safety, toxicity, and effect of treatment. Will communicate with principal investigators and study personnel at all sites and run monthly study teleconferences with the Study Coordinator. Will oversee any changes to the protocol and will be responsible for submitting amendments to the appropriate regulatory agencies (such as IRB, DSMB, sponsors, FDA, etc.). [See also Appendix D]

WCMC Co-Investigators ([name], [name], NP, [name], [name], [name], [name] NP, [name]): Responsible for patient recruitment, overall clinical management, assessment of adverse events, safety, toxicity, and effect of treatment. Will assist with protocol design, coordination, and interpretation of scans.

Nuclear Medicine Chairs ([name], [name]): Responsible for administration of IND agents (radiolabeled J591 antibodies) for diagnostic and therapeutic studies, will oversee evaluation and quantitation of radiolabeled J591 scans. Will oversee quality control of radiolabeled antibody.

Statistician ([name], MS, Dr.PH): Assist with study design, data analysis and interpretation, assist with protocol amendments.

Research Nurse Assist with patient recruitment, study drug administration, documentation of adverse events.

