5.4 Duration of Follow Up

Patients will be followed for 3 years after removal from study or until death, whichever occurs first. Patients removed from study for unacceptable adverse events will be followed until resolution or stabilization of the adverse event.

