7.5 Secondary AML/MDS

Myelodysplastic syndrome and acute myeloid leukemia has been reported in patients previously treated with anti-CD20 based RIT for non-hodgkin's lymphoma. Some case reports and small series have raised concern for this phenomenon after RIT (116). However, given the increased incidence of MDS/AML in this population, either because of their underlying illness or of their exposure to previous cytotoxic therapy (especially alkylating agents), there is no good evidence

to suggest that there is a significantly increased risk than of a similar population of patients not receiving RIT (117, 118). However, based upon the theoretical increased risk, the incidence of MDS/AML during follow up will be noted and used to increase the investigators' experience and knowledge. Any suspected potential increased risk of MDS/AML will be reported to the IRB and DSMB.

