¹ Baseline radiographic evaluation should be performed within one month of enrollment (or following enrollment as part of screening). Subsequent scans (CT/MRI abd/pelvis, CXR (or CT chest), and bone scan) should be performed every 6 months until PSA progression, then every three months thereafter unless clinically indicated sooner.

² CBC repeated twice a week when platelets <25,000/mm³ and/or ANC <500/mm³

³ CBC's not associated with study visits may be performed at any CLIA certified laboratory

⁴ The same lab should be used for all study PSA's if possible

⁵ CTC counts via CellSearch (using kit) at C1D1 prior to ketoconazole, C2D1 (prior to Lu-J591), C3D1, at the time of PSA progression, and at end of study. Additional blood samples for CTC analysis for research will be drawn at C1D1 prior to treatment and at end of study

⁶ Adrenal hormone levels should be drawn prior to starting treatment on Cycle 1, Day 1, 1 month, and at PSA progression

⁷ Starting after C1D1 assessment and blood draw until toxicity, investigator, or patient decision as per Sections 5.2.1, 5.2.2, 6.1. Distribute medication diary at the beginning of each cycle.

⁸ Visit 3 (C2D1): Targeted physical exams can be completed the day prior to the scheduled J591 infusion date.

⁹ All references to targeted physical exams throughout the protocol include a heart and lung examination, as well as evaluation of any abnormalities found during the complete physical exam performed at screening

¹⁰ Vital signs include temperature, heart rate, blood pressure, and respiratory rate.

¹¹ The End of Study Visit occurs when patient shows evidence of metastatic disease. Patient remains on trial until documented metastatic disease. In addition to scans a biopsy can be performed to prove metastatic disease. Patient can receive additional therapy prior to showing metastatic disease and still remain on trial. Site will be asked for information regarding the additional therapy in the case report forms.

¹² In the event that the J591 infusion is delayed, cycle 1 will be extended until the date of the J591 infusion. The date of the J591 infusion will be considered Cycle 2, Day 1.

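### Toxicity is reported as crude proportions over a window that ends at metastasis, so frequencies of events that accumulate over time would be expected to run higher in the 177Lu-J591 arm even at equal rates

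*Combined protocol and SAP*

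**What the plan says.** All places are in the combined protocol and SAP.

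- **Start of the window.** Section 13.5.1 counts toxicity from first treatment and, for the antibody, says "Toxicity of radiolabeled J591 in this population will be evaluated from the time of J591 administration". Neither sentence gives an end.
- **End of collection.** The study calendar and section 10.1 list adverse events at the recurring visits up to EOS, at PSA progression and at EOS itself. EOS is defined as metastasis appearing on scans.
- **Other treatment inside the window.** Footnote 11 of the calendar says "Patient can receive additional therapy prior to showing metastatic disease and still remain on trial". Section 5.3 keeps such men in 3-monthly follow-up and has the later therapies documented.
- **Analysis.** Section 13.4 says "The frequency of subjects experiencing toxicities will be tabulated", with exact 95% confidence intervals on the proportions. It mentions no exposure adjustment, fixed risk window, censoring at new therapy or time-to-event analysis of toxicity.
- **Late marrow disease.** Section 7.5 says "the incidence of MDS/AML during follow up will be noted and used to increase the investigators' experience and knowledge", and section 5.4 says "Patients will be followed for 3 years after removal from study or until death, whichever occurs first".

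**The concern.** The denominator in 13.4 is subjects, but how long each subject is observed depends on when he metastasizes. If 177Lu-J591 delays metastasis as hoped, its arm is observed for longer and has more time to record any event that keeps occurring: background illness, ketoconazole or hydrocortisone effects, late effects. A crude proportion then shows an excess that reflects longer observation and not a higher rate. Events caused by a later anti-cancer drug fall in the same window.

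The toxicity of single-dose 177Lu-J591 plus ketoconazole, and the toxicity of high-dose ketoconazole, are both secondary objectives in section 1.2. The randomized control arm is the natural yardstick for the first of these, and unequal windows weaken it.

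**Working it through.** **Inputs from section 13.1:** 18-month MFS of "80% vs. 50%, respectively" (177Lu-J591, control); about 34 and 17 patients; "a one-sided alpha level of 10" percent; at least 80% power; minimum observation 18 months; MFS described up to 36 months. **Assumed, because the documents give none:** a constant adverse event rate r, equal in both arms, from 0.005 to 0.10 per month.

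**Step 1. Reproduce the plan's figure.** Pooled proportion = (17 × 0.5 + 34 × 0.8)/51 = 0.70. Null SE = √(0.21 × (1/17 + 1/34)) = 0.1361. Alternative SE = √(0.25/17 + 0.16/34) = 0.1393. Power = Φ((0.30 − 1.2816 × 0.1361)/0.1393) = Φ(0.901) = 81.6%. The stated power holds, so 80% versus 50% is a fair statement of what the plan expects. The plan gives no figure for the toxicity window itself.

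**Step 2. Length of the window.** Treat the MFS event as the end of collection, with constant hazard λ = −ln(MFS)/18.
- Control: ln 2/18 = 0.0385 per month. 177Lu-J591: −ln(0.8)/18 = 0.0124 per month.
- Mean window to month T = (1 − e^(−λT))/λ.
- T = 18: 13.0 versus 16.1 months (ratio 1.24). T = 36: 19.5 versus 29.0 months (ratio 1.49).

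**Step 3. Crude frequency at equal rates.** P = r/(r + λ) × (1 − e^(−(r+λ)T)). In the scan-detected version, the window runs to the first 6-monthly scan at or after metastasis, or to T. Cells show control, 177Lu-J591 and the gap in percentage points (from unrounded values).

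| r per month | 18 months | 36 months | Gap at 18, 6-monthly scans | Gap at 36, 6-monthly scans |
|---|---|---|---|---|
| 0.005 | 6.2%, 7.7%, +1.5 | 9.1%, 13.4%, +4.3 | +1.0 | +3.7 |
| 0.01 | 12.0%, 14.8%, +2.8 | 17.0%, 24.7%, +7.7 | +1.9 | +6.6 |
| 0.02 | 22.3%, 27.3%, +5.0 | 30.0%, 42.5%, +12.5 | +3.4 | +10.5 |
| 0.05 | 45.0%, 54.1%, +9.1 | 54.2%, 71.7%, +17.5 | +5.9 | +13.9 |
| 0.10 | 66.2%, 77.2%, +11.0 | 71.7%, 87.4%, +15.7 | +6.5 | +11.0 |

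Scans move to every 3 months after PSA progression, so detection in practice should lie between the two versions.

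**Step 4. Later therapy.** This was simulated with r = 0.02 and the event rate multiplied 2- to 5-fold once another therapy starts. Control men were assumed to start it at 0.08 per month.
- Same start rate in both arms: the 18-month gap widens to +7.1 to +10.5 points.
- Control men start 2 to 3.2 times sooner (177Lu-J591 arm at 0.04 or 0.025 per month): the 18-month gap runs from +3.5 to −4.6 points, and the 36-month gap from +12.7 to +5.5.

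**Step 5. What the alternatives do.**
- Fixed window: at 3 months from the start of treatment, about the time of C4D1 (day 85), the gap in the step 3 model is 0.1 to 0.9 points across all rates. At 6 months it is 0.2 to 2.9, or zero with 6-monthly scan detection.
- Rate per patient-month: P divided by the mean time to first event or end of window, (1 − e^(−(r+λ)T))/(r + λ), equals r in both arms.

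**The case against.** **Acute toxicity.** A reader might infer that 177Lu-J591 will look more toxic across the board. The documents do not support that. Section 5.2.2.1 expects the lowest platelet count four to five weeks after infusion, routine scans start at 6 months, and section 10.1 keeps weekly blood counts going for men not recovered by C4D1. The main antibody toxicity is therefore counted almost equally in both arms.

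**Later drugs.** A reader might also infer that later therapy always adds to the 177Lu-J591 count. Step 4 shows the sign can reverse at 18 months. Section 7.2 also requires attribution of every event, and the trial is double-blind. That helps, but 13.4 does not limit its table to related events, so how far later-drug events enter it is left open.

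**MDS/AML.** A reader might infer from the calendar, whose last column is EOS, that recording stops at metastasis. Sections 7.5 and 5.4 read together already extend it through the 3-year follow-up. Adding 36 months to the step 2 windows and ignoring deaths, mean time at risk is 49.0 versus 52.1 months (6% longer on 177Lu-J591) or 55.5 versus 65.0 (17%). The 24% and 49% differences do not carry over.

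**Weight.** No between-arm toxicity test is planned. At r = 0.03 the model gives 38% versus 31% at 18 months, roughly 13 of 34 and 5 of 17, with exact 95% intervals of 22–56% and 10–56%. An artefact of that size sits well inside the reported uncertainty. The event rates are assumed, visits thin out to every 12 weeks after ketoconazole stops, and 36 months is only a descriptive time point for MFS.

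These points limit the scope and the weight of the concern. They do not remove the core: no stated end, an outcome-dependent window and crude proportions.

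**Conclusion.** The point holds for events that accumulate over time. If the trial succeeds as planned, the 177Lu-J591 arm is observed about 24% longer over 18 months and 49% longer over 36. At equal true rates of 0.5% to 10% per month, its crude frequencies would be expected to exceed control by 1.5 to 11.0 points at 18 months, or 1.0 to 6.5 with 6-monthly scan detection. At 36 months the ranges are 4.3 to 17.5 and 3.7 to 13.9.

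These sizes rest on constant hazards, on the plan's own MFS target being met, on equal and constant event rates, and on no change in event rate after new therapy. If the arms do not differ in MFS, the artefact disappears. The harm is to the interpretation of a secondary objective. Type I error and the primary comparison are untouched. The documents support neither a general claim that the better arm looks more toxic nor a claim that MDS/AML recording ends at metastasis.

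**What to change.** In sections 13.4 and 13.5.1:

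1. Report J591 toxicity by arm in one equal, fixed window from infusion, for example to C4D1 (8 weeks), with cytopenias followed to recovery as 10.1 already requires.
2. Report longer-term and ketoconazole toxicity by arm per patient-month or as time to first event, censored at the start of another anti-cancer therapy or at EOS, whichever comes first. Time to first event is safer where rates change over time. Both approaches assume that event risk is not strongly tied to the reason for censoring, and the text should say so.
3. List events after new anti-cancer therapy separately.
4. At most, for MDS/AML, add time at risk by arm to what 7.5 and 5.4 already provide.

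No new visits are needed: adverse events are already logged visit by visit and later therapies are already documented. The cost is wording, a few extra tables, and late events moving to a table of their own.
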